13.3. Effectiveness

"3.1.1 Changes in Mayo score (Observed Case)"

Patients for analysis: patients in the effectiveness analysis group

Analysis objective: to show Mayo score and the changes in Mayo score per assessment period.

Analysis item: calculate the number of patients in the analysis groups.

Calculate the number of target patients, the mean and standard deviation of Mayo score, the mean and standard deviation of changes in Mayo score for each assessment period, and conduct a paired-t test which compares the values at the initial administration.

Note: Follow "12.3 Assessment period for Mayo score" for Time Allowance of assessment period.

The analysis covers only the patients with the assessment applicable to Time Allowance of the first administration and each assessment period.

Multiplicity in the test will be adjusted by the Bonferroni method.

"3.1.2 Changes in the remission rate at each point of Mayo score (Observed Case)"

Patients for analysis: patients in the effectiveness analysis group

Analysis objective: to show the remission rate of Mayo score per assessment period.

Analysis item: calculate the number of patients in the analysis groups.

Calculate the number of target patients, the percentage to the number of patients who achieved a remission and the number of target patients, 95%CI of the remission rate, and conduct a McNemar test for the first administration per assessment period.

In addition, prepare a line plot to describe the percentage to the target patients among the patients who achieved a remission per assessment period.

X-axis: assessment period (in week)

Y-axis: percentage (%)

Note: Follow "12.3 Assessment period for Mayo score" for Time Allowance of assessment period.

The analysis covers only the patients with the assessment applicable to Time Allowance of the first administration and each assessment period.

For the confidence interval, use the Clopper-Pearson's confidence interval.

Refer to "10.3 Effectiveness analysis" for the calculation method and remission rate.

"3.1.4 Changes in partial Mayo score (Observed Case)"

Patients for analysis: patients in the effectiveness analysis group

Analysis objective: to show partial Mayo score and the changes in partial Mayo score per assessment period.

Analysis item: calculate the number of patients in the analysis groups.

Calculate the number of target patients, the mean and standard deviation of partial Mayo score, the mean and standard deviation of changes in partial Mayo score for each assessment period, and conduct a paired-t test which compares the values at the initial administration.

In addition, calculate the mean of the mean days to the final assessment and the standard deviation.

Note: Follow "12.4 Assessment period for partial Mayo score" for Time Allowance of assessment period.

The analysis covers only the patients with the assessment applicable to Time Allowance of the first administration and each assessment period.

Multiplicity in the test will be adjusted by the Bonferroni method.

"3.1.5.1 Changes in the remission rate at each point of partial Mayo Score (Observed Case)"

Patients for analysis: patients in the effectiveness analysis group

Analysis objective: to show the remission rate of partial Mayo score per assessment period.

Analysis item: calculate the number of patients in the analysis groups.

Calculate the number of target patients, the percentage to the number of patients who achieved a remission and the number of target patients, 95%CI of the remission rate, and conduct a McNemar test for the first administration per assessment period.

In addition, prepare a line plot to describe the percentage to the target patients among the patients who achieved a remission per assessment period.

X-axis: assessment period (in week)

Y-axis: remission rate (%)

Note: Follow "12.4 Assessment period for partial Mayo score" for Time Allowance of assessment period.

The analysis covers only the patients with the assessment applicable to Time Allowance of the first administration and each assessment period.

For the confidence interval, use the Clopper-Pearson's confidence interval.

Refer to "10.3 Effectiveness analysis" for the calculation method and remission rate.

"3.1.5.2 Changes in the remission rate (NRI) at each point of partial Mayo Score"

Patients for analysis: patients in the effectiveness analysis group

Analysis objective: to show the remission rate of partial Mayo score per assessment period.

Analysis item: calculate the number of patients in the analysis groups.

Calculate the number of target patients, the percentage to the number of patients who achieved a remission and the number of target patients, 95%CI of the remission rate, and conduct a McNemar test for the first administration per assessment period.

In addition, prepare a line plot to describe the percentage to the target patients among the patients who achieved a remission per assessment period.

X-axis: assessment period (in week)

Y-axis: remission rate (%)

Note: Follow "12.4 Assessment period for partial Mayo score" for Time Allowance of assessment period.

The analysis covers only the patients with the assessment applicable to Time Allowance of the first administration and each assessment period.

For the confidence interval, use the Clopper-Pearson's confidence interval.

Refer to "10.3 Effectiveness analysis" for the calculation method and remission rate.

NRI: when it is unknown whether the remission is achieved, impute the data without remission.

"3.1.7.1 Remission rate at Week 52 in patients who achieved a remission at Week 8 of administration based on partial Mayo score"

Patients for analysis: Patients in the effectiveness analysis group (the patients who did not achieve a remission when the administration was started but achieved the remission at Week 8 of administration in partial Mayo score)

Analysis objective: to show the remission rate of partial Mayo score at Week 52 of administration in patients in the analysis group.

Analysis items: calculate the number of target patients, the percentage to the number of patients who achieved a remission at Week 52 of administration and the target patients, and the confidence interval of the remission rate. (calculate them in both Observed Case and NRI patterns)

Note: the patients for analysis should have partial Mayo score at the first administration and Week 8 of administration and achieved a remission at Week 8 of administration except those who had already achieved a remission in partial Mayo score at the first administration.

Follow "12.4 Assessment period for partial Mayo score" for Time Allowance of assessment period.

For the confidence interval, use the Clopper-Pearson's confidence interval.

"3.1.7.2 Remission rate at Week 52 in patients who achieved the response as an index of partial Mayo score at Week 8 of administration"

Patients for analysis: Patients in the effectiveness analysis group (the patients who achieved a response at Week 8 of administration in partial Mayo score)

Analysis objective: to show the remission rate of partial Mayo score at Week 52 of administration in patients in the analysis group.

Analysis items: calculate the number of target patients, the percentage to the number of patients who achieved a remission at Week 52 of administration and the target patients, and the confidence interval of the remission rate. (calculate them in both Observed Case and NRI patterns)

Note: the patients for analysis should have partial Mayo score at the first administration and Week 8 of administration and be a responder at Week 8 of administration.

Follow "12.4 Assessment period for partial Mayo score" for Time Allowance of assessment period. For the confidence interval, use the Clopper-Pearson's confidence interval.

Definition of responder: partial Mayo score at every assessment decreases by 2 points or more and by 30% or more. In addition, at least one of the following conditions shall be met.

- Rectal bleeding score has been decreased by at least 1 point since the administration was started.
- Rectal bleeding score is ≤ 1 .

"3.2 General improvement rate"

Patients for analysis: patients in the effectiveness analysis group

Analysis objective: to show the general improvement rate at Week 52 or at discontinuation of administration

Analysis item: calculate the number of patients in the analysis groups.

For the general improvement rate at the final observation which was calculated according to "12.5 Assessment period of general improvement rate", calculate the percentage to the number of patients and the patients in the analysis group per "general improvement rate" and "detailed classification for patients with an effective or better result in general improvement rate" defined in "11 How to stratify data".

"3.4 Aggregation for effectiveness per patient background factor (general improvement rate)" Patients for analysis: patients in the effectiveness analysis group

Analysis objective: to show the effectiveness rate of the general improvement rate at Week 52 or at discontinuation of administration as the primary endpoint and analyze the factors.

Analysis items: calculate the number of patients, the percentage to the number of patients with an effective (markedly effective + effective) in general improvement rate and all patients, the

percentage to the number of patients with an ineffective result in general improvement rate and the number of all patients, the tests for effectiveness (Fisher's exact test for nominal-scale factors and Man-Whitney's u test for ordinal-scale factors) per the following patient background factor.

Note: the patient background factors are as follows:

Age (year), the elderly, pediatrics, sex, body weight (kg), BMI (kg/m²), duration of illness (year), complications, complication: hepatic function disorder, complication; renal impairment, complication: blood disorder, complication: respiratory disorder, complication: diabetes mellitus, complication: osteoporosis, complication: malignant tumour, medical history; medical history: tuberculosis, medical history: non-tuberculous mycobacteriosis, medical history: interstitial pneumonia, medical history: bronchitis bacterial, medical history: aplastic anaemia, medical history: pancytopenia, medical history: malignant tumour, allergy history, smoking history, detailed history of smoking history, the administration status of Humira: self-administration, prior medication, prior medication: biological product, prior medication Infliximab, prior medication: other biological product, prior medication: aminosalicylic acid drug, prior medication: corticosteroids, prior medication: azathioprine, prior medication 6-mercaptopurine, prior medication: azathioprine & 6-mercaptopurine, prior medication: tacrolimus & ciclosporin, prior treatment, prior treatment: leukocytapheresis, prior treatment: surgery, prior treatment: enteral nutrition therapy, prior treatment: intravenous nutrition therapy, concomitant medication, concomitant medication: aminosalicylic acid drug, concomitant medication: corticosteroids, concomitant medication: azathioprine, concomitant medication: 6-mercaptopurine, concomitant medication: azathioprine & 6-mercaptopurine, concomitant medication: tacrolimus & ciclosporin, concomitant treatment, concomitant treatment: leukocytapheresis, concomitant treatment: surgery, concomitant treatment: intravenous nutrition therapy, concomitant treatment: enteral nutrition therapy, site of disease by type, partial Mayo score, CRP

"3.4.1 Aggregation for effectiveness per patient background factor (partial Mayo score)" Patients for analysis: patients in the effectiveness analysis group

Analysis objective: to show the remission of partial Mayo score at the final assessment as the primary endpoint per patient background factor and analyze them.

Analysis items: calculate the number of all patients, the percentage to the number of patients who achieved a remission in partial Mayo score and all patients, the number of patients who failed to achieve a remission in partial Mayo score and the percentage to number of all patients, the tests for remission (Fisher's exact test for nominal-scale factors and Man-Whitney's u test for ordinal-scale factors) per the following patient background factor:

Note: Refer to "3.4 Aggregation for effectiveness per patient background factor (general improvement rate)" for patient background factors.

"3.5 Changes in CPR level"

Patients for analysis: patients in the effectiveness analysis group

Analysis objective: to show measured CPR levels at each assessment period.

Analysis items: calculate CRP's summary statistics (number of cases, mean, standard deviation, minimum value, 1st quartile value, the median, 3rd quartile value and the maximum value) per assessment period.

Note: Follow "12.6 Assessment period for CRP" for Time Allowance of assessment period.

The analysis covers only the patients with the assessment applicable to Time Allowance of the first administration and each assessment period.

"3.6 The status of corticosteroid use and the remission in partial Mayo score in patients who used corticosteroids when administration was started (Observed Case)"

Patients for analysis: patients in the effectiveness analysis group

Analysis objective: to show the status of corticosteroid use and with/without remission in partial Mayo score per assessment period in patients who concomitantly used corticosteroids when administration was started

Analysis items: calculate the number of target patients, the percentage to the number of patients with/without concomitant use of corticosteroids and to the number of target patients, and the percentage to the number of patients who achieved/failed to achieve a remission in partial Mayo score and to the number of target patients.

Note: The target patients to be counted in each assessment period shall receive Humira in each Time Allowance defined in "12.4 Assessment period of partial Mayo score".

The target patients who concomitantly used corticosteroids at each assessment period shall receive corticosteroids at each scheduled date defined in "12.4 Assessment period of partial Mayo score".

Follow "12.4 Assessment period for partial Mayo score" for Time Allowance of the assessment period regarding with/without remission in partial Mayo score.

"3.7 Endoscopy results during administration period"

Patients for analysis: patients in the effectiveness analysis group

Analysis objective: to show endoscopy results at each assessment period.

Analysis item: calculate the number of patients in the analysis groups.

Calculate the number of patients who underwent endoscopy, the number of patients with endoscopy results (normal, remission mucosa, mild, moderate and severe), and the percentage to the patients who underwent endoscopy per assessment period.

Note: Follow "12.3 Assessment period for Mayo score" for Time Allowance of assessment period. The analysis covers only the patients with the assessment applicable to Time Allowance of the first administration and each assessment period.

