HUMIRA® for Subcutaneous Injection Protocol for Special investigation on Long-Term administration Ulcerative Colitis

AbbVie GK

1. Purpose of Surveillance

The following were investigated in the Special investigation on Long-Term administration of "HUMIRA® for Subcutaneous Injection (Nonproprietary name: Adalimumab (Genetical Recombination)" in patients with ulcerative colitis.

- 1. Unknown adverse drug reactions (ADRs) (especially important ADRs)
- 2. Incidence and conditions of occurrence of adverse reactions in the clinical setting
- 3. Factors that may affect the safety and efficacy of Humira
- < Priority items of investigation >

Infection, tuberculosis, malignant tumor, injection site reaction, autoimmune disease, pancytopenia, demyelinating disorders, congestive cardiac failure, and interstitial pneumonia For enteral infection, the cause (virus or bacteria) will be examined.

2. Sample Size

The number of patients to be included: 1500

They are patients with ulcerative colitis who use this drug after approval.

- < Rationale for setting >
- 1. Since this survey will be conducted in actual clinical practice, the proportion of patients who have been treated with anti-TNF α products is anticipated to be high. First, considering that a dropout rate may be higher than that in Japanese clinical studies due to the enrollment of such patients, the planned sample size was calculated by assuming a dropout rate at Week 52 of 70%. Next, in the all-case survey in patients with Crohn's disease, the CDAI, an efficacy endpoint, was not recorded for approximately 30% of all the patients. Thus, by assuming the proportion of patients without assessment of Mayo score of 30%, a remission rate of 30% and the accuracy of 95% confidence interval estimation of \pm 5%, the sample size was determined to be 1500 patients (Table 1).

Table 1 Sample size calculated based on the dropout rate and accuracy

Dropout rate 70%					
Sample size	Sample size at Week 52	No. of patients assessed for Mayo score	Remission rate 30% at Week 52 95%CI	Accuracy	
500	150	105	21.2~38.8	±8.8%	
1000	300	210	23.8~36.2	±6.2%	
1500	450	315	24.9~35.1	±5.1%	
2000	600	420	25.6~34.4	±4.4%	

No. of patients assessed for Mayo score is calculated 70% of sample size at Week 52.

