2. Next, for the presence or absence of history of use of anti-TNFα products, the accuracy of the remission rate used for setting the above sample size of 1500 patients was evaluated (Table 2). The following conditions were specified for the evaluation:

In data from the all-case survey of Humira in patients with Crohn's disease, 80% and 20% of the patients had used and had not used anti-TNF α products. Immediately after the drug was approved for Crohn's disease, because there were many patients waiting for the drug such as non-responders to anti-TNF α products in previous treatment, patients are likely to be enrolled in the present survey at the same ratio. Therefore, the rate for the use of anti-TNF α products in the survey was selected to be 80% and 20% for patients have used and have not used them.

The remission rate based on the Mayo score at Week 52 was set to 10% for patients who have used anti-TNF α products based on data from an overseas clinical study (M06-827) and 30% for patients who have not used them which was utilized for calculating the above sample size of 1500 patients.

Table2 Remission rate of history of anti-TNFα products use

	No. of patients	Remission		
	assessed for	rate at	95%CI	Accuracy
	Mayo score	Week 52		
History of anti-TNFα products	252	10%	6.1~13.9	±3.8%
use	232	10%	0.17~13.9	±3.8%
Without history of use of anti-	62	200/	17.9~42.1	±12.1%
TNFα products	63	30%	17.9° ~42.1	±12.1%

Based on these results, while the accuracy is poor because the number of patients in the group without history of use of anti-TNF α products is small, the data from the group with a history of use of anti-TNF α products is assumed to be an assessable numerical value (Table 2).

In a domestic clinical study of this drug in patients with ulcerative colitis (Study M10-447: 52 weeks), adverse events occurred in one patient where the incidence rate was 0.6% (1/177). On the basis of this incidence, when 1500 patients are accumulated, the 95% confidence interval for the incidence would be 0.3 to 1.1% and assessable. Even if the incidence of tuberculosis is 2%, which is higher than that in the clinical study, in this survey, by accumulating 1500 patients, the upper and lower limit of the confidence interval would be 2.84 and 1.35, respectively. Hence, because the incidence of tuberculosis (as an adverse event) shown in the Japanese clinical study in patients with rheumatoid arthritis is higher than 1.0%, it is evaluable.

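### Full Mayo remission at Week 52, the effectiveness endpoint behind the 1500-patient target, is planned only as an observed-case rate, with no non-responder-imputation counterpart

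*SAP*

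**What the plan says.** **Sizing.** Protocol Section 2 sets the target: "The number of patients to be included: 1500". Its rationale states that "the planned sample size was calculated by assuming a dropout rate at Week 52 of 70" per cent, and then arrives at 1500 "by assuming the proportion of patients without assessment of Mayo score of 30%, a remission rate of 30" per cent, with a 95% interval of about ±5 points. The footnote to Table 1 explains the assessed number: "No. of patients assessed for Mayo score is calculated 70% of sample size at Week 52". For the split by anti-TNFα history, "The remission rate based on the Mayo score at Week 52 was set to 10% for patients who have used" such products, and to 30% for the others (Table 2: 252 and 63 patients). SAP Section 4.3 repeats both tables.

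**Full Mayo analysis.** SAP Section 13.3 has one table of full Mayo remission rates: "3.1.2 Changes in the remission rate at each point of Mayo score (Observed Case". Its note restricts each row to patients with a score in the baseline window and in the window of that row. Section 10.3 counts a full Mayo score only if every component, endoscopy included, was assessed. Section 9.1 rules out imputation except where a later item definition provides for it, and Table 3.1.2 provides for none.

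**Partial Mayo analysis.** Section 13.3 plans an observed-case table (3.1.5.1) and also "3.1.5.2 Changes in the remission rate (NRI) at each point of partial Mayo Score", in which unknown remission status counts as no remission. Tables 3.1.7.1 and 3.1.7.2 likewise ask for both patterns.

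**The concern.** The plan expects most patients to be missing from the Week 52 row of the endpoint it was sized on, and expects most of those to be dropouts. SAP Section 11 lists lack of effectiveness among the reasons for discontinuation, so being missing is plausibly related to outcome. A rate among those still followed and fully scored can then look favourable, and the line plotted from Table 3.1.2 can rise simply because non-remitters leave the denominator. For partial Mayo, the reader gets a second figure that shows how far this matters. For full Mayo at Week 52 there is none.

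**Working it through.** **Inputs.** From Protocol Section 2: N = 1500; dropout at Week 52 of 70%; 30% of the remainder without a Mayo score; remission 30% overall, or 10% (252 patients) and 30% (63 patients) by anti-TNFα history. The documents do not give the size of the effectiveness analysis group or how many patients have a baseline full Mayo score, so 1500 as a denominator is an assumption.

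**1. Reproduce Table 1.**
- Remaining at Week 52: 1500 × (1 − 0.70) = 450.
- Assessed: 450 × (1 − 0.30) = 315.
- Half-width: 1.96 × √(0.30 × 0.70 / 315) = 5.06 points, so 24.9% to 35.1%. This matches the stated row, and the other three rows also reproduce.

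**2. Coverage of the Week 52 row.**
- 315 / 1500 = 21%.
- Outside it: 1500 − 315 = 1185. Of these, 1500 − 450 = 1050 (89%) are dropouts and 450 − 315 = 135 (11%) are followed but not scored.
- Table 3.1.2 also needs a baseline score, so 315 is a ceiling on these assumptions. With baseline scores in 90% or 70% of patients (assumed), it falls to about 284 or 221.

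**3. Observed case against NRI.**
- Remitters among observed patients: 0.30 × 315 = 94.5.
- Observed case: 94.5 / 315 = 30%.
- NRI: 94.5 / 1500 = 6.3%. Clopper-Pearson limits are 5.1% to 7.6% with 94 remitters and 5.2% to 7.7% with 95.
- With a denominator of 1200 and the same remitters: 94.5 / 1200 = 7.9%.
- With the Table 2 mix: 0.10 × 252 + 0.30 × 63 = 25.2 + 18.9 = 44.1 remitters. Observed case is 44.1 / 315 = 14.0%; NRI is 44.1 / 1500 = 2.9%.
- Restricting both rates to patients with a baseline score leaves the percentages unchanged if baseline availability is unrelated to follow-up and outcome. For example, with 90% available, (0.9 × 94.5) / (0.9 × 1500) = 6.3%.

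**4. How much depends on the missing patients.**
- Dropouts counted as failures, but the 135 unscored stayers remitting at 30%: 0.30 × 450 / 1500 = 9.0%.
- All 1185 missing patients failing, or all remitting: 94.5 / 1500 = 6.3% to (94.5 + 1185) / 1500 = 85.3%. This is the range without any assumption about them.

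**5. The final-assessment row as a substitute.** Suppose 30% to 70% of the 1050 dropouts have a complete score at discontinuation and 0% to 10% of those remit (both assumed; Week 24 scores ignored). The pooled observed rate then runs from 94.5 / 1050 = 9% to (94.5 + 31.5) / 630 = 20%. It moves in the expected direction, but it depends on how many dropouts are scored and it is not a Week 52 rate.

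**The case against.** The case for leaving the plan alone has substance.

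- **Full Mayo at Week 52 is not designated primary.** The SAP attaches that term to general improvement (Table 3.4) and to partial Mayo remission at final assessment (Table 3.4.1). A reader might take Table 3.1.2 for the headline result; the documents do not call it that. It remains the effectiveness endpoint used to justify the sample size.
- **Dropouts are not ignored.** Section 12.3, which Table 3.1.2 follows, defines discontinuation and final-assessment periods for full Mayo, and the case report form collects Mayo score and endoscopy at discontinuation (Protocol Section 8). The SAP also plans a Kaplan-Meier continuation rate (1.6.2), reasons for discontinuation (1.7) and NRI for partial Mayo. This stands, but the extra full Mayo rows are again observed case, need a complete score, and do not give a Week 52 rate on the whole group. Partial Mayo is a different endpoint, without endoscopy.
- **The row is not simply patients on drug.** A reader might infer that. However, a discontinued patient is one whose last dose falls before first dose + 336 days (SAP Section 10.1), and the window is Day 337 to 393, so a recent discontinuer can be scored in it. Patients who change hospital count as discontinued even if treatment continues, and stayers without a complete score are left out.
- **NRI on full Mayo is harsh in routine practice.** A followed patient who had no endoscopy becomes a non-remitter, so the rate partly measures how often patients are scoped. This is a fair reason to treat NRI as a sensitivity analysis, not as a replacement.
- **Counts are already planned.** Table 3.1.2 reports the analysis group and the target patients in each period, so the shrinking denominator will be visible. The reasons for missing scores will not be.

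**Conclusion.** The gap is real but narrow. The full Mayo remission rate at Week 52 is planned only as observed case, on at most about 315 of 1500 patients (21%) by the plan's own assumptions, and it lacks the NRI counterpart given to partial Mayo. Whether it overstates remission depends on missing patients remitting less often than observed ones. That is plausible but not established, since the SAP also lists improvement of the condition among the other reasons for stopping. If every missing patient counts as a non-remitter, 30% becomes 6.3% (7.9% with 1200 patients), and 14.0% becomes 2.9% with the Table 2 mix.

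A reader might go further and treat the observed-case rate as an upper bound, with the truth between 6.3% and 30%. The documents do not support that: without an assumption about the missing patients, the range is 6.3% to 85.3%. All these figures are projections from planning assumptions, not results. The point is a cheap improvement to the reporting; it does not invalidate the planned analysis.

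**What to change.** Add an NRI version of Table 3.1.2 at Weeks 24 and 52, with Clopper-Pearson intervals, printed beside the observed-case rows and labelled as a sensitivity analysis.

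- State the denominator explicitly: all effectiveness-group patients with a baseline full Mayo score, whether or not they have a score in the later window.
- Show the number missing at each time, split into discontinued and still followed but not fully scored.
- Do not carry over the note in Table 3.1.5.2 that limits the analysis to patients with a score at baseline and in each window. Read literally, it removes the very patients NRI is meant to impute.

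The cost is one extra table, using an imputation rule the SAP already states for partial Mayo and which Section 9.1 permits once defined in Section 13.3. The drawback is that NRI is conservative, because followed patients without endoscopy count as non-remitters. The text should therefore ask the reader to consider the two rates together and not as limits on the true rate.
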